4.3.1 Examination position

The examining position to be used in the field for young children will be the classic pediatric ophthalmic examination technique. With the aid of a helper seated directly opposite to the examiner, the child will be positioned with his/her head between the examiner's knees, with the child's face looking upwards toward the examiner. The legs of the child will be straddled across the helper and the arms held gently across the child's chest. Care should be taken to keep the child's eyes above the level of the examiner's knees, in order to properly take the conjunctival swab.

4.3.1 Everting the upper eyelid

For all participants, only the right upper eyelid will be examined for this study. The only exception to this is if the right eye is difficult to examine due to eye disease or injury, in which case the left eye will be examined. In order to avoid passing contamination from the child into the eye, once the examiner dons a new pair of gloves, their gloved hands should not be used to position the child. The examiner uses their fingertips to grasp the central portion of the participant's upper lid eyelashes. The upper lid is then everted, using a finger of the examiner's other hand (or the end of a sterile swab) as a fulcrum, positioned superior to the tarsal plate.

The everted lid is held in place by the examiner's non-dominant hand holding the eyelashes against the orbital rim.

4.3.3 Conjunctival photography

Specific team members will be designated as photographers for the entire trial in order to ensure high quality photographs by an experienced photographer. The photographer will take photographs of the conjunctiva with a handheld Nikon D90 digital camera with a macro lens (1:1). Conjunctival photography causes no damage to the eye, is well tolerated by children, and is a standard clinical procedure at UCSF. Photographs will be identified by first taking a photograph of the 6-digit random identification sticker that was assigned to the child during the registration phase of the study visit. By convention, all photos taken after this random number (up to the next photographed random number) belong to the preceding random number. If a random number is mistakenly not photographed before taking a photograph of the conjunctiva, it may be photographed afterwards; in this case, a note should be included that says "preceding photos." Photographs are stored on the memory card in the camera, and then transferred to an external hard drive each night. Batteries are charged each night; each camera bag has at least 2 spare batteries.

Photography Protocol

- Equipment needed: camera, labels, photo log book, and CD burner
- Miscellaneous equipment: Extra battery, card reader, lens filter, extra media card

Camera Setup

A handheld Nikon D-series camera and lens will be used for all photographs. If possible, use natural light rather than a flash, as the flash introduces artifacts into the image.

- Model
 - Nikon D-series camera: D-40, 50, 70, 80, 90, 100 or 200
 - There are minor differences between the different models, mostly related to setup
- Lens
 - Nikon Macro Autofocus 105 mm f/2.8
- Settings
 - Manual setting- turn off autofocus
 - Disengage "limit" engage "full"
 - Extend lens to 1:1; note with older versions of this lens it is 1:1 at full extension; newer versions can go to slightly higher magnification than 1:1 so caution must be exerted
 - Image size/resolution
 - Jpg normal- set thru "setup" menu
 - Large- set thru "setup" menu ("small and medium" are probably adequate)
- White balance- automatic or flash; set thru "setup" menu
- Shutter- Aperture Priority
- f57- set thru menu; note if lens is not extended to 1:1, f57 will not be allowed

- ISO 400

Photograph Procedure

- Place patient into position that will allow maximum stability; standing, sitting or “head-clamp” position. Employing village volunteer to help is very useful.
- Take photo of patient ID
- Image is brought into focus by changing the working distance, not by turning the lens. This is because the lens is fixed in its manual setting. The working distance is approximately 20 cm from the eye with our current settings
- Take minimum of 2 photos. If there is any doubt of the quality of the photo while the patient is in position it is better to continue to take more photographs before the patient is allowed to leave. It is easy to delete photos if they are not needed.
- Check photos before allowing child to leave. If they are not acceptable, repeat procedure. Only stop if the patient or guardian requests that we stop, or if is deemed impossible, even with further attempts. Note we have obtained >95% acceptable photos in previous studies.
- If the child cannot be photographed for some reason, it does not affect the eligibility of the child. A notation is made on the ocular form of why the photograph cannot be taken, but no replacement is sought. Again, this is expected to be a rare event.

Photo Troubleshooting Guide

Note all camera settings are permanently embedded in every photo that is taken and can be viewed with the camera or with any standard commercial photo-viewing software (e.g., Adobe Photoshop; Photomechanic, Nikon View, Canon, etc.)

- Photos too DARK, too LIGHT or OUT OF FOCUS
 - Check camera settings: ISO 400, Aperture preferred, +/- on zero, Manual setting on lens, flash elevated; battery fully charged
- If all photos are affected in the same way than it is most likely the settings on the camera or lens
 - Change camera settings from default recommendations
 - Decrease F stop to lighten, increase to darken
 - Could be taken down to 32 or lower but depth of field will be lessened
 - +/- can be increased or decreased to change exposure (+ to lighten; - to darken)
 - Check that lens is on Manual NOT Autofocus
 - ISO- increase to lighten photo, decrease to darken
 - Very high ISO will produce graininess
 - Meter- try “spot” instead of “pattern”
 - Have another person observe photography in real time
 - Make sure flash is not depressed by photographer or someone else while photo is taken. (This commonly happens if photographer has loupes). Is the lens well supported?
 - Make sure battery is fully charged

- If first photos in series are acceptable and then they gradually become less exposed (darker) it might be because the battery is gradually losing power during the session. Note that the flash reaction time increases as the battery power decreases.
- Out of focus
 - F stop may be too low; movement artifact; flash doesn't work; lens is dirty
- Image not centered
 - Movement of child or camera (hold child's head between knees of "helper"; stabilize camera with second hand)
- Reflection artifact
 - Move camera slightly between first and second photos to achieve different angle; gently dab conjunctiva with swab- must be done at periphery to avoid creating inflammation

Grading of clinical conjunctival photographs

Three experienced ophthalmologists will grade the photographs at the conclusion of the study. Graders will grade each photograph in the set for follicles and inflammation according to the WHO simplified grading system.

4.3.4 Clinical evaluation of the conjunctiva

On site clinical examination will be performed by medical staff member previously trained. The examiner will use the 2.5X magnifying ocular loupes (Wilson ophthalmics) to assess the tarsal conjunctiva of the everted upper right eyelid. The examiner will grade the conjunctiva according to the WHO simplified Trachoma grading scale (see table below). If necessary, a hand-held torch light will be used by the examiner for illumination of the conjunctiva. The examiner tells the Trachoma Grade to the tuber, who then records the grade onto the electronic device. Field staff will only be certified to grade for the study if they exceed sufficient agreement with an expert trachoma grader ($\kappa \geq 0.6$ on a series of 25 pictures) during the training session.

Definitions of the WHO Simplified Trachoma Grading Scale

TF (Trachomatous Inflammation – Follicular): the presence of five or more follicles in the upper tarsal conjunctiva.

TI (Trachomatous Inflammation – Intense): pronounced inflammatory thickening of the upper tarsal conjunctiva that obscures more than half of the normal deep tarsal vessels.

TS (Trachomatous Scarring): the presence of scarring in the tarsal conjunctiva.

TT (Trachomatous Trichiasis): at least one eyelash rubs on the eyeball.

CO (Corneal Opacity): easily visible corneal opacity over the pupil.

Clinically active trachoma: defined as either **TF** or **TI**. If WHO guidelines recommend that **TF** alone is the most appropriate sign to follow, then we will easily be able to report this.

5. ANTHROPOMETRY

Anthropometry will be collected for all children in Study Two at baseline and 4 weeks after the completion of the treatment. We will measure length or height, weight, and MUAC.

Measuring Length and Height

A lightweight measuring board will be used to measure the participant's height to the nearest 0.1 cm. Height will be assessed with a ShorrBoard. Depending on a child's age and ability to stand, measure the child's length or height.

Length: If a child is less than 2 years old, or cannot stand alone, measure recumbent length. A child's length is measured lying down (recumbent).

Height: If a child is able to stand, we will measure standing height.

Procedure

If the child has braids or hair ornaments that will interfere with length/height measurements, remove them if possible. Check that any sandals, shoes, or socks have also been removed.

Whether measuring length or height, the mother/guardian is needed to help with measurements and to soothe and comfort the child. Explain to the mother the reasons for the measurements, and describe the steps in the procedure. Answer any questions she might have. Show her and tell her how she can help you. Explain that it is important to keep the child still and calm to obtain the best measurement.

ShorrBoard Set-Up

- 1) Remove ShorrBoard from bag.
- 2) Stand the ShorrBoard upright. You can step on the base of the board to keep it stable.
- 3) As you face the board, turn the non-removable bolt counterclockwise to release the extension piece. Note: the bolt remains attached to the back of the extension piece – do NOT remove it.
- 4) Slide the extension piece into the top end of the main board and fasten the clasp on the back of the board. Make sure the clasp is fastened properly.
- 5) The auto-lock sliding head/footpiece is stored in the base of the main board and can be moved up and down the length of the measuring board. It should stay in place on its own wherever you position it.
- 6) The measuring board must be placed against a firm surface for standing height (e.g. wall, table, tree, against a vehicle, etc.). Make sure the board is stable. If necessary, place items such as small rocks underneath the height board to stabilize it during the measurement.
- 7) Clean the equipment with alcohol swabs at the beginning of each day.

Note: when you set up the board each day, examine each of the pieces to check for damage.

[figure not shown]
Measure Length

Cover the length board with a cloth for hygiene and for the baby's comfort. Explain to the mother that she will need to place the baby on the length board and then help to hold the baby's head in place while the measurement is taken. Show her where to stand when placing the baby down (i.e. opposite you, on the side of the length board away from the tape). Also show her where to place the baby's head (against the fixed headboard) so that she can move quickly and surely without distressing the baby. When the mother understands your instructions and is ready to assist: Ask her to lay the child on his back with his head against the fixed headboard, compressing the hair.

Quickly position the head so that an imaginary vertical line from the ear canal to the lower border of the eye socket is perpendicular to the board. (The child's eyes should be looking straight up.) Ask the mother to move behind the headboard and hold the head in this position. Speed is important. Standing on the side of the length board where you can see the measuring tape and move the footboard: Check that the child lies straight along the board and does not change position. Shoulders should touch the board, and the spine should not be arched. Ask the mother to inform you if the child arches the back or moves out of position. Hold down the child's legs with the one hand and move the footboard with the other. Apply gentle pressure to the knees to straighten the legs as far as they can go without causing injury or distress.

Note: it is not possible to straighten the knees of newborns to the same degree as older children. Their knees are fragile and could be easily injured, so apply only minimum pressure.

If a child is extremely agitated and both legs cannot be held in position, measure with one leg in position. While holding the knees, pull the footboard against the child's feet. Upon reading the measurement, the examiner will clearly call out the number to the recorder. Record the child's length in centimeters to the last completed 0.1 cm. (1.0 mm). Keeping the child in place, release the sliding footboard, and prepare to repeat the measurement. Re-position the child for a second and third measurement.

[figure not shown]

Measure Standing Height

Ensure that the height board is on level ground. Working with the mother, and kneeling in order to be at the level of the child. Help the child stand on the baseboard with the weight of the child evenly distributed on both feet. The heels of the feet are placed together with both heels touching the base of the vertical board. Place the feet pointed slightly outward at a 60 degree angle. The back of the head, shoulder blades, buttocks, calves, and heels should all touch the vertical board. Arms should hang freely by the sides of the body with the palms facing the thighs.

Note: Standing with all body parts touching the board may be difficult for some children, in which case, help the child to stand on the board with one or more contact points touching the board.

Ask the mother to hold the child's knees and ankles to help keep the legs straight and feet flat, with heels and calves touching the vertical board. Ask her to focus the child's attention, soothe the child as needed, and inform you if the child moves out of position. Position the child's head so that a horizontal line from the ear canal to the lower border of the eye socket runs parallel to the baseboard. Ask the child to inhale deeply and to stand fully erect without altering the position of the heels. If necessary, push gently on the belly to help the child stand to full height. Still keeping the head in position, use your other hand to pull down the headboard to rest firmly on top of the head and compress the hair. Upon reading the measurement, the examiner will clearly call out the number to the recorder. Record the child's height in centimeters to the last completed 0.1 cm (1.0 mm). Keeping the child in place, release the sliding headboard, and prepare to repeat the measurement. Re-position the child for a second and third measurement.

Dismantling the ShorrBoard

- 1) Stand the board upright: face the board and step on the base with one foot to keep it stable.
- 2) Slide the head/footpiece into the base of the main board.
- 3) Release the clasp on the back of the extension piece and remove it. Push the clasp FLAT against the extension piece.
- 4) To attach the extension piece to the main board, turn the front of the extension piece inward and place it against the front of the main board. Make sure that all sides of the extension piece are straight and in line with the main board.
- 5) Push on the bolt that is on the back of the extension piece and screw it into the main board.
- 6) Put the board back inside of the carrying case for storage until your next use.

Measuring Weight

The SECA 874 scale will be used to weigh infants and children to the nearest 0.01 kg. Infants and young children can also be weighed simultaneously with their parent or guardian by the unique “mother-baby” function (parent or guardian is weighed and then the infant or child is weighed while held by the parent). Explain to the mother that we want to weigh her child to see how he or she is growing. If she has a baby or a child who is unable to stand, she will hold the child on the scale. If the child is 2 years or older/can stand alone, the child will be weighed alone. Children should be wearing only light clothing, no shoes or sandals, no hair ornaments, and no jewelry. Explain that the child needs to remove outer clothing and shoes/sandals in order to obtain an accurate weight. If the baby is wearing a diaper, the diaper should be removed. If any heavy clothes remain on the child, make a note in the Notes section.

Seca 874 Scale

- 1) Remove scale from bag.
- 2) Be sure that the scale is placed on a flat, hard, even surface. All 4 legs of the scale should make contact with the ground surface, without wobbling. It may be helpful to place a piece of plywood on the ground underneath the scale.
- 3) When **batt** appears in the display, you should change the batteries. Remove the old batteries and insert 6 new batteries.

Turn the power on the scale when you are ready to begin weighing. If the child is unable to stand on the scale, you will use the 2 in 1 weighing function (called tared weighing). The 2 in 1 function enables the weight of babies and small children to be determined while an adult holds them. Identify a suitable area that is flat for horizontal placement of the scale. Press the start key with no load on the scale. The scale is ready for use when it sets to 0.00. If necessary, switch the weight display to KG: hold down the 2 in 1 key for about 3 seconds. Press the start key with no load on the scale. Wait until the display shows 0.00.

Ask the adult to remove his/her shoes and stand in the middle of the scale without the child. S/he should remove any long garments, as these can cover the display and also lead to variable measurements. After the adult's weight appears on the display, tell him/her to remain standing on the scale. Press the 2 in 1 key to activate the function. The scale stores the weight of the adult and the display returns to zero. When 0.00 and NET appear in the display, hand the child to the adult. The scale will determine the weight of the child. Once the value is stable for about 3 seconds, the weight is measured.

Note: If an adult is very heavy (e.g. more than 100 kg) and the baby's weight is relatively low (e.g. less than 2.5 kg), the baby's weight may not register on the scale. In such cases, have a lighter person hold the baby on the scale.

The positioner will clearly call out the child's weight to the recorder. Record the child's weight to the nearest 0.01 kg. Repeat the measurement 2 more times. Note that only the baby needs to be removed from the scale; the adult should remain on the scale the entire time. To turn off the 2 in 1 function, press the 2 in 1 key. The 2 in 1 function remains on until you press the 2 in 1 key again, or until the scale switches off automatically. If several children are to be weighed consecutively with the same adult holding the babies, it is important that this person's weight does not change (e.g. due to a piece of clothing being removed/added). If the child is able to stand on the scale, you will weigh the child alone. Talk with the child about the need to stand still. Communicate with the child in a sensitive, non-frightening way. Press the start key with no load on the scale. The scale is ready for use when it sets to 0.00. Ask the child to stand in the middle of the scale. Once on the scale, the child must stand still. The HOLD function is automatically activated for weights over 1.5 kg/3.3 lbs. The display flashes until a stable weight has been measured. The display is then frozen until the next weighing operation.

Note: If the child jumps on the scale or won't stand still, you will need to use the tared weighing procedure instead.

The positioner will clearly call out the child's weight to the recorder. Record the child's weight to the nearest 0.01 kg. Repeat the measurement 2 more times. Have the child move completely off the scale and then stand again on the scale. If no further weighing operations are performed, the scale switches off automatically after 2-3 minutes.

Scale Calibration

In order to monitor the calibration of the scales over time, each team will weigh a 5 kg test weight at the beginning and end of the day. This measurement will take place at the site of the scale storage so that the weights do not need to be carried to the field. In some cases, these weights will be kept in a project vehicle.

[figure not shown]
Measuring Mid-Upper Arm Circumference (MUAC)

The child's MUAC will be measured one time. MUAC measurements will be taken at the midpoint of the left arm between the tip of the shoulder and the tip of the elbow using non-stretch MUAC tapes.

First, find the approximate midpoint of the upper arm. Have the child stand up straight with feet together, and the right arm bent 90 degrees at the elbow, palm facing up. The examiner is positioned behind the child. If it is helpful, mark the midpoint with a permanent marker. To measure mid-upper arm circumference, have the child stand up straight with the arms relaxed at the sides. The examiner will stand facing the child's right side. The measuring tape is placed around the upper arm at the marked point. Wrap the tape around the arm, pulling it to lie flat against the surface of the skin. Be careful not to pull the tape too tightly (to compress the skin).

The line for reading measurements is clearly labeled on the MUAC tape (READ (cm)). Read the number aligned with the measurement line on the tape. Upon measuring, the examiner will clearly call out the number to the recorder. Record to the nearest 0.1 cm (0.1 cm = 1 mm). Keeping the child in place, release the MUAC strip.

If the MUAC is <11.5cm refer the child to the nearest health center.

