To determine if there are differences in nutritional outcomes across treatment arms one month following treatment, we will calculate weight-for-height (WHZ), weight-for-age (WAZ), and height-for-age (HAZ) Z-scores based on 2006 WHO standards. We will compare mean WHZ, WAZ, HAZ, and mid-upper-arm circumference (MUAC) across treatment arms as continuous variables adjusting for baseline anthropometric values using an ANCOVA. We will also compare

the prevalence of stunting (HAZ <-2 SD) and moderate (WHZ <-2 SD) and severe (WHZ <-3 SD) acute malnutrition across study arms with a logistic regression model.

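### MUAC, a baseline-adjusted secondary outcome, is read once per visit while length, height and weight are read three times: a modest, cheaply avoided loss of precision, not a bias

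*Protocol*

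**What the plan says.** Protocol section 5 (Anthropometry) sets a different number of readings for different measures.

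- **Length and standing height:** after the first reading, "Re-position the child for a second and third measurement". The same instruction closes both procedures.
- **Weight, child held by an adult:** "Repeat the measurement 2 more times. Note that only the baby needs to be removed from the scale".
- **Weight, child standing alone:** "Repeat the measurement 2 more times. Have the child move completely off the scale and then stand again on the scale".
- **MUAC:** "The child's MUAC will be measured one time". The resolution is "Record to the nearest 0.1 cm (0.1 cm = 1 mm").

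MUAC has two uses. Under Secondary Outcomes the SAP states: "We will compare mean WHZ, WAZ, HAZ, and mid-upper-arm circumference (MUAC) across treatment arms as continuous variables", with ANCOVA adjustment for the baseline value. Section 5 also says: "If the MUAC is <11.5cm refer the child to the nearest health center".

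The documents do not say how the three length, height or weight readings are combined. They give no MUAC reading error, standard deviation or observer-standardisation step, and no reason for the single reading.

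**The concern.** The repeat readings go to the measures that seem to need them less. Weight comes from an electronic scale that freezes a stable value, records to 0.01 kg and is checked with a 5 kg test weight at the start and end of each day. MUAC depends on where the examiner judges the midpoint to be, on an optional skin mark and on how tightly the tape is pulled. Elsewhere the protocol does control observers: field graders of trachoma must reach a kappa of at least 0.6 before they are certified. MUAC has neither repeat readings nor a standardisation check.

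In an ANCOVA the reading error acts twice. It adds variance to the 4-week value, and it weakens the baseline covariate, which then removes less of the between-child variation. With 30 households per arm and no power calculation for any outcome, precision that can be had at existing visits is worth having. What is at stake is the width of the interval for one secondary outcome.

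**Working it through.** **The plan's own figures.** 120 households / 4 arms = 30 per arm, as Protocol 3.2.1 states. There is no alpha, power, effect size or SD, so there is no precision figure for MUAC to reproduce.

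**Inputs from the documents.** One MUAC reading per visit; two visits (baseline and 4 weeks after treatment); recording to 0.1 cm; baseline-adjusted ANCOVA; 30 per arm.

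**Assumptions, not in the documents.** Between-child SD s = 1.2 cm; single-reading error SD e = 0.1, 0.2 or 0.3 cm, independent between readings; true baseline-to-follow-up correlation ρ = 0.80 to 0.98.

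**Formulas.** Let v be the error variance of the value used at each visit.

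- One reading: v = e² + 0.1²/12, where the second term is rounding.
- Median of three normal readings: about 0.449 times that. (The mean would give 0.333 times.)
- With equal true SDs at both visits, residual variance = (s² + v)·[1 − (ρs²/(s² + v))²].
- Written with a true 4-week change of SD c, residual variance = s² + c² + v − s⁴/(s² + v), and ρ = s/√(s² + c²).

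**One case in full: e = 0.2, c = 0.35.**

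- ρ = 1.2/√(1.44 + 0.1225) = 0.96.
- One reading: v = 0.04 + 0.0008 = 0.0408. Residual variance = 1.44 + 0.1225 + 0.0408 − 2.0736/1.4808 = 0.203.
- Median of three: v = 0.449 × 0.0408 = 0.0183. Residual variance = 1.44 + 0.1225 + 0.0183 − 2.0736/1.4583 = 0.159. Simulation with readings rounded to 0.1 cm gives 0.160.
- Cut: 1 − 0.160/0.203 = 21%. Ratio: 0.203/0.160 = 1.27, the same gain as 27% more children.

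**Range, by simulation with rounding (cut in residual variance, one reading to median of three).**

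| True correlation | e = 0.1 cm | e = 0.2 cm | e = 0.3 cm |
|---|---|---|---|
| 0.80 | 2% | 6% | 12% |
| 0.90 | 3% | 11% | 20% |
| 0.94 (c = 0.45) | 5% | 15% | 25% |
| 0.96 (c = 0.35) | 8% | 21% | 32% |
| 0.98 (c = 0.25) | 13% | 30% | 40% |

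**In centimetres.** For 30 against 30 children, two-sided 5% and 80% power (also assumed), the detectable difference is (1.96 + 0.84) × SD × √(2/30) = 0.723 × SD.

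- e = 0.2, ρ = 0.96: from 0.723 × √0.203 = 0.33 cm to 0.723 × √0.160 = 0.29 cm.
- e = 0.2, ρ = 0.80: residual variance 0.586 against 0.550, so from 0.55 cm to 0.54 cm.

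**If the readings share a midpoint.** Section 5 allows the midpoint to be marked on the skin. Error in placing that mark is then common to all three readings and does not average out. If half the error variance is shared, v for the median is (0.5 + 0.5 × 0.449) × 0.0408 = 0.0296. Residual variance is 1.44 + 0.1225 + 0.0296 − 2.0736/1.4696 = 0.181, and the cut drops from 21% to 1 − 0.181/0.203 = 11%.

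**The case against.** The best defence is that nothing here is inconsistent. The single reading is an explicit instruction, MUAC is one of several anthropometric secondary outcomes, and the primary outcome (Simpson's index) is untouched. The larger gains also need a correlation of about 0.94 to 0.98; at 0.80 to 0.90 the cut is 6% to 11% for an error SD of 0.2 cm and 2% to 3% for 0.1 cm. All of that stands and limits the weight of the point. It does not remove it, because the improvement is nearly free and the documents give no reason for treating MUAC differently.

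Three stronger readings are tempting, and the documents support none of them.

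- **That the MUAC comparison is biased.** Reading error that does not depend on arm leaves the randomised difference in means unbiased. Error in the baseline value only weakens the adjustment.
- **That length, height and weight are protected by averaging and MUAC alone is not.** No rule for combining the triplicate readings is stated, so the contrast is in the number of readings taken, not in a demonstrated reduction of error.
- **That a single reading undermines referral.** MUAC is not the only route: Protocol section 8 also refers children with wasting or stunting. The numbers are small too. Take 240 children (two per household, the count in Protocol section 6), an assumed mean of 14.0 to 14.5 cm, SD 1.2 to 1.3 cm and error SD 0.1 to 0.3 cm. The expected number of children classified wrongly at 11.5 cm, in either direction, is 0.3 to 2.9 with one reading and 0.2 to 1.6 with the mean of three. With mean 14.5 cm, SD 1.2 cm and error SD 0.2 cm, the median of three would save about 0.05 of a missed child per visit.

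**Conclusion.** The point holds as a minor one on precision. Reading MUAC once gives up between about 2% and 40% of ANCOVA residual variance relative to the median of three. At an error SD of 0.2 cm the loss is 6% to 21% over correlations of 0.80 to 0.96. At 0.1 cm it is small, 2% to 8% over the same correlations. Every figure rests on the assumed between-child SD, reading error and correlation, and on independent errors, so each is an upper bound if a marked midpoint is shared. There is no bias and no effect on the primary outcome, and no finding about referral is made.

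The same subsection has a separate defect that repeat readings would not cure. It names the left arm for the measurement, but bends the right arm to find the midpoint and has the examiner face the child's right side. These sentences contradict each other and must be reconciled.

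**What to change.** In Protocol section 5, replace the single-reading sentence with: MUAC is measured three times at baseline and three times at 4 weeks; the tape is removed and the midpoint located afresh before each reading, without relying on an earlier skin mark; all three values are recorded. In the SAP, state that the median of the three is the value used at each visit in the MUAC ANCOVA. If the sponsor prefers one reading, it should state the expected MUAC reading error that makes one sufficient.

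The cost, as a judgement rather than a documented figure, is about one minute per child per visit and two more tablet fields. No new equipment, staff or visit is needed.

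No proposal is made on how the referral decision is taken. If three readings are adopted, the sponsor will need to say how the existing referral sentence applies to them.

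Separately, reconcile the left-arm and right-arm instructions in the MUAC subsection, and say there or in the SAP how the triplicate length, height and weight readings are combined.
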